Data were collected on-line via a free and open iOS application, “DiagnosUs”, created by Centaur Labs as a platform for game-like image labeling competitions <https://www.centaurlabs.com/>). Between 6/22/21 and 6/27/21, Centaur Labs ran 24 ‘contests’ on our behalf, collecting >300,000 trials from 803 participants in 6 days. Each of the 24 contests consisted of 80 unique images of a skin lesion as shown in Figure 1. This is a relatively small number of images, but it kept the sessions short and encouraged participation. Images came from the International Skin Imaging Collaboration (ISIC) 2018 challenge (Codella, et al., 2019). The set contains over 1,200 melanoma images and over 7,600 nevus images.

[figure not shown]

Figure 1: Sample stimulus displays. Left: Participants are asked if a lesion is a melanoma (cancer) or a nevus (benign ‘mole’). Right: After response, if this were a feedback condition, red or green feedback would inform the observer of the correctness of the answer. In no feedback conditions, neutral feedback indicated that the response had been registered.

On each of the six days, there were four contests available. These were:

- 1) Low Prevalence – No Feedback; consisting of 20% (16) melanoma images
- 2) Low Prevalence – Feedback; prevalence was the same as in #1, but with accurate, trial by trial feedback
- 3) High Prevalence – No Feedback; consisting of 50% (40) melanoma images
- 4) High Prevalence – Feedback; prevalence was the same as in #3, but with accurate, trial by trial feedback

The contests were randomly assigned to participants with the constraint that they did not run the same type of contest more than once in a day. Participants could take part in as many or as few contests as they wished over the course of the six days and they could end up repeating a

condition from one day on another day. The prevalence and feedback conditions were not advertised to participants. Accuracy is the main dependent variable though we also collected response times.

Because of the on-line, voluntary nature of the data collection, we did not have control over the viewing conditions or the type of screen used. We compensated by collecting a very large dataset (see below).

Observers

We collected data from 803 unique individuals. For each individual, we have a crude categorization of expertise as shown in Table 1:

Medical Student	337
Pre-Med Student	174
No Medical Experience	145
Medical Doctor	54
Other Healthcare Professional	47
Nurse	25

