Medical Technician	11
Physician Assistant	10

Table 1: Observers divided by expertise category

Participants were asked why they chose to participate and given three choices, as shown in Table 2.

Compete With Others	37
Earn Money	248
Improve My Skills	518

Table 2: Observers divided by reason to participate

Participants reported coming from 78(!) countries with three quarters of the participants coming from nine countries, as shown in Table 3.

Philippines	198
USA	182
Ghana	94
Great Britain	31
Romania	30
Canada	27
Mexico	19
Indonesia	15
Australia	13
All other	194

Table 3: Reported country of origin.

Beyond this demographic information, we have only an observer number. We were given no identifying information about the participants. Participation on the app constituted consent. Procedures were approved by the Institutional Review Board at Brigham and Women's Hospital (IRB #2007P000646).

These 803 participants produced 311,842 trials of data. An excel spreadsheet with all data is posted on the Open Science Framework at <https://osf.io/hck5n/>. From this set, we eliminated participants who did not complete a full block of 80 trials. This left 630 participants who ran a total of 277,371 trials in 2,988 blocks. Different participants chose to participate in different numbers of blocks. As shown in Table 4.

Blocks Run	# of Participants		Blocks Run	# of Participants
1	315		13	10
2	178		14	2
3	104		15	4
4	56		16	6
5	52		17	5
6	22		18	3
7	27		19	10
8	20		20	3
9	14		21	4
10	10		22	2
11	10		23	6
12	5		24	4

Table 4: Numbers of participants who ran N (1-24) blocks over 6 days of testing.

Those participants running only a single block were removed from most analyses because our primary interest is the influence of one block upon the next. Obviously, with some participants contributing 24 blocks and others contributing 2, the dataset is unbalanced. We repeated the main analyses reported below, limiting the analysis to only the first pair of blocks for each observer. This reduces power. However, the main patterns of results, reported below, are found when the dataset is restricted to only blocks 1 and 2. Accordingly, we think that the unequal numbers of trials and blocks from different participants is not a significant issue for the present study. In the results reported, we analyze results from the 2,998 remaining blocks of data.

Statistical Analysis / Results

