To analyze the effect of one block on the next block, we derived all the pairs of blocks in the dataset. For each of the blocks, we calculated the true positive and false positive proportions and used these to derive the standard signal detection measure of d' and criterion (Note that we are refraining from using the term “sensitivity” because it is used to refer to d' in the behavioral science community and to the true positive rate in the medical community.) For the primary analyses, pairs were removed from analysis if either member of the pair produced a d' of less than 0.5. The task was relatively difficult and we had little control over the motivation of participants in online study of this sort. The probability of achieving a $d' > 0.5$ by guessing through an 80 trial block is $\sim 0.6\%$. A cutoff of 0.4 would permit over 2% of blocks to be pure guessing. A $d' > 0.5$ cutoff left 2,080 pairs of blocks. The distribution of those pairs is shown in

Table 5:

		Block N				
		Low, No Feedback	Low, Feedback	High, No Feedback	High, Feedback	
Block N+1	Low, No	29	140	151	134	454
	Low, Feed	92	110	150	218	570
	High, No	261	117	51	117	546
	High, Feed	147	218	118	27	510
		529	585	470	496	2080

Table 5: Counts of the 16 different pairs of Block N and Block N+1.

As can be seen, there is a good, if uneven distribution of pairs. There are fewer pairs on the diagonal where the condition is the same in Blocks N and N+1. In order to run the same block, twice in a row, participants needed to encounter that condition last on Day K and first on Day K+1 since the same condition could not be run twice on the same day. The marginals show that this distribution of the four different conditions is very roughly uniform.

First, we compare performance in the four conditions, regardless of their position the sequence of sessions for each observer. Figure 2 shows the signal detection measures of d' and criterion, “c”. These values cannot be computed if $p(\text{True Positive}) = 1.0$ or $p(\text{False Positive}) = 0.0$. Accordingly, in keeping with one standard practice, we add $\frac{1}{2}$ of a False Positive error to each False Positive count (Hautus, Macmillan, & Creelman, 2021).

[figure not shown]

Figure 2: D' and Criterion as a function of condition. Each dot represents one of 2080 blocks of data. Black lines show mean and +/- 95% CI of the mean.

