first half and second half of the trials in block 2, separately. The results are essentially unchanged from those shown in Figure 5. Exposure to Low Prevalence with Feedback in block 1, produces a conservative shift in block 2 criterion in both the first half and the second half of block 2. All t-tests for pairs where Block 1 is Low Feedback are significant except for the Low Feedback → High Feedback pair in the first half, when the effect should be stronger than in the second half. Exposure to High Prevalence with Feedback in block 1, produces a liberal shift in block 2 criterion in both the first half and the second half of block 2. T-tests when block 2 is Low Feedback, Low No Feedback and High No Feedback are significant. T-test when block 2 is High Feedback is not significant in either half (again, recall that the High Feedback -> High Feedback pair has the fewest instances in the dataset).

The lack of any systematic decrease in the magnitude of the effects is shown in Figure 8. The mean change in criterion is plotted for the first and second half of each pair of blocks. Note the grouping of the pairs. The dark blue pairs show the conservative (positive) shift following low prevalence with feedback. The red pairs show the liberal (negative) shift following high prevalence with feedback. If the effects only lasted for the first 2-3 dozen trials, these effects should collapse toward zero in the second half. Clearly, this is not the case.

[figure not shown]

Figure 8: Mean change in criterion for the first and second halves of a block of trials.

Effects of Expertise

As noted in the Methods section, participants gave a rough categorization of their level of expertise. Sadly, this convenience population does not include any substantial number of self-identified expert dermatologists. Only one MD self-identifies as a dermatologist. We can create an expertise continuum from participants reporting no medical training to premedical students to medical students and, finally, to medical doctors. Table 6 shows the numbers of participants and the number of pairs of data contributed by each group.

Expertise category	No. of Participants	No. of pairs
Medical Doctor	54	131
Medical Student	337	952
Pre-Med Student	174	426
No Medical Experience	145	358

Table 6: Number of participants in each expertise group and the number of condition pairs contributed by the groups.

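### The completeness rule is written for participants, not blocks, so in some of the 2,080 pairs Block N may not be the contest that immediately preceded Block N+1

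*Combined protocol and SAP*

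**What the plan says.** In the Specific Protocol, the Methods section fixes the length of a block: "Each of the 24 contests consisted of 80 unique images of a skin lesion". The Observers section then gives the data flow. It starts from the full set ("These 803 participants produced 311,842 trials of data"), applies one completeness rule ("we eliminated participants who did not complete a full block of 80 trials") and reports the result: "This left 630 participants who ran a total of 277,371 trials in 2,988 blocks". The same section closes with a different block count: "we analyze results from the 2,998 remaining blocks of data". Table 4 is captioned "Numbers of participants who ran N (1-24) blocks over 6 days of testing".

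Under Statistical Analysis / Results, pairing is described in one line: "we derived all the pairs of blocks in the dataset". The only further filter for the primary analyses removes a pair if either block has a d' below 0.5, which concerns performance and not completeness. No section gives a rule for the unfinished blocks of a retained participant.

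Two later steps take an analysed block to be 80 trials long: the guessing rate of about 0.6% that justifies the d' cutoff, and the analysis of the "first half and second half of the trials in block 2, separately".

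**The concern.** The study asks what the preceding block does to the next one, and the condition of Block N is the only exposure behind the main finding in Figure 5. As written, the rule removes a person who never finished a block and keeps everyone else with everything they started.

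Take a participant who finishes contest A, abandons a feedback contest B part-way, and then finishes contest C. There are three possible treatments:

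- **B is scored as a block.** The labels are right, but the exposure is shorter than 80 trials and d' and criterion are noisier. A low-prevalence block has only 16 melanomas even when complete.
- **B is passed over.** The pair is recorded as A to C, although the last exposure was B.
- **B breaks the sequence.** No pair is formed and no label is wrong.

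Only the second treatment misstates the exposure. The more-than-two-hours subset in Figure 7, which carries the persistence claim, deserves particular care, because a longer gap leaves more room for an uncounted block.

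**Working it through.** **Inputs** (all from the Specific Protocol). Methods: 80 images per contest. Observers: 803 people and 311,842 trials before exclusion; 630 people, 277,371 trials and 2,988 blocks after it; 2,998 blocks at the end of the section; and the cells of Table 4. Statistical Analysis / Results: 2,080 pairs after the d' filter.

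**1. Can the retained trials be rebuilt from the block counts?** Trials = blocks x 80, compared with 277,371.

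| Block count | Source | x 80 | Trials left over | Share of 277,371 |
|---|---|---|---|---|
| 2,988 | Observers, after exclusion | 239,040 | 38,331 | 13.8% |
| 2,998 | Observers, last sentence | 239,840 | 37,531 | 13.5% |
| 3,409 | Sum of Table 4 | 272,720 | 4,651 | 1.7% |
| 3,094 | Table 4 without its 315 one-block participants | 247,520 | 29,851 | 10.8% |

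None matches. The stated figures imply 277,371 / 2,988 = 92.8 trials per block (92.5 with 2,998), above the maximum of 80.

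**2. Does any number of complete blocks fit?** 277,371 = 3,467 x 80 + 11. The retained trials are therefore not all in complete blocks, whichever block count is right. This needs only that 277,371 is printed correctly and that each image is answered once per contest.

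**3. Could scored part-blocks explain the excess?** No. Counted blocks hold at most 80 trials each, so if 2,988 is right, at least 38,331 trials lie outside the counted blocks. That fits part-blocks left out of the count better than part-blocks scored within it.

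**4. Is there room for interrupted pairs to have been dropped?** A person with k blocks in sequence gives k - 1 consecutive pairs, so the maximum is blocks minus people.

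- 2,988 - 630 = 2,358. With 2,080 retained, 278 pairs (11.8%) were lost to the d' filter and any breaking of pairs together.
- 2,998 - 630 = 2,368, so 288 (12.2%) were lost.
- Table 4: 3,409 - 872 = 2,537, so 457 (18.0%) were lost.

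On the stated counts there is little room for widespread dropping of interrupted pairs, though some is possible.

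**5. Are the counts reliable enough to size the problem?** No. Table 4 sums to 872 people, more than the 630 retained and more than the 803 enrolled. The left-over trials run from 4,651 to 38,331 depending on which count is used. Turning them into a number of part-blocks needs a mean length that the documents do not give.

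**6. Likely direction if blocks were passed over.** A hidden feedback block after a no-feedback Block N would add carry-over to pairs reported as showing almost none. A feedback Block N followed on the same day by a hidden feedback block would be followed by one at the other prevalence, because a contest type could not be run twice in a day. Both would tend to weaken the reported contrast. Across days the hidden block could repeat Block N's condition, so the direction is less clear there.

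**The case against.** The strongest reply is that the documents show a missing rule and untidy counts, not a mislabelled pair. Five points can be made.

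- **The treatment is unknown.** The introduction to the Specific Protocol describes pairings of consecutive blocks, which is compatible with dropping interrupted pairs. A part-block after a person's last complete block affects no label. This stands: a reader might infer that the exposure is shown to be wrong, but no document reports a bridged pair.
- **The rule can be read otherwise.** It might mean that anyone who left any block unfinished was removed, so that only complete blocks remain. The remainder of 11 speaks against this.
- **The excluded group fits the person-level reading awkwardly.** The 173 people removed (803 - 630) account for 34,471 trials (311,842 - 277,371), about 199 each. At no more than 79 trials per unfinished block, that is at least 2.5 abandoned contests per person on average. Either abandonment was frequent or the counts are wrong. The point does not show that retained people were free of part-blocks.
- **Any error probably works against the finding.** Clear effects after feedback and almost none without it are not what dilution would create. This is fair for Figure 5, and less secure for gaps that span days.
- **Robustness was checked.** Removing the d' filter and restricting to each person's first pair are both reported. Both take the block sequence as given, so neither tests this point.

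A reader might also infer that differential quitting has biased the comparison. Completion of Block N+1 does come after exposure, but completion by condition is not reported, so this is a possibility and not a result.

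**Conclusion.** The concern holds as a gap in the definition of the exposure. The completeness rule is stated for people, the retained trials cannot all be in complete 80-trial blocks, and nothing says whether unfinished blocks were scored, bridged over or used to break pairs. Block N may therefore not be the immediately preceding exposure in some of the 2,080 pairs.

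The remainder of 11 needs only that the trial total is printed correctly and that each image is answered once. The excess of 38,331 trials also needs 2,988 to be correct, and Table 4 contradicts that count while being impossible in its own total of people. The number of affected pairs cannot be derived, and a percentage of affected blocks would rest on an assumed length. Dilution is the likelier effect, but it is not established.

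This is more than a missing detail, because the main finding and the persistence result both depend on what the preceding block was, and the check can be made on data that the Observers section says are posted.

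**What to change.** 1. Apply the completeness rule per block. Order every started block, finished or not, by time within participant. Form a pair only from two complete 80-trial blocks adjacent in that order, and exclude pairs with a part-finished block between them.
2. State how part-finished blocks were treated in the reported analysis, and how many of the 2,080 pairs change or drop out, by cell of Table 5.
3. Report the rates of starting and of completing Block N+1 by Block N condition.
4. Rerun Figures 5 and 7 on the adjacent-pair set, at least as a sensitivity analysis.
5. Reconcile 2,988, 2,998 and Table 4 (872 people, 3,409 blocks) with each other and with 277,371 trials.

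Keeping shorter Block N+1 records, for example those with 40 trials on the model of the half-block analysis, is not advised. Halving the trials raises the SD of d' by about 40% (the square root of 80/40 is 1.41), and the d' cutoff is justified for 80 trials.

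No new data are needed. The cost is the loss of some pairs, which will hurt most in small cells such as the 27 High Feedback to High Feedback pairs. Excluding interrupted pairs is itself conditional on quitting, and the rates in item 3 would show whether that differs by condition.

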Figure 9 shows d' and criterion as a function of expertise group, regardless of the type of feedback or prevalence (Recall, from Figure 2, that there is little effect of block type on d' .)

[figure not shown]

Figure 9: Effects of expertise category on d' and crit, regardless of prevalence and/or feedback.

There is a highly significant effect of expertise category ($F(3, 1863) = 38.58, p < 0.0001$, partial eta-squared = 0.86) and, as can be seen by the pairwise comparisons, that effect is entirely due to superior performance of the medical students (all comparisons to medical students, $p \leq 0.0001$).

It might seem disappointing that MDs were no better at this task than non-medical participants.

However, these non-dermatologist MDs may not have spent time looking at skin lesions for many years and the novices were only being asked to perform a difficult, but straight-forward, two-alternative, forced-choice discrimination. It is the medical students, many of whom may have recently been learning about skin lesions, who do somewhat better on this task. Of course, there could be other reasons for the group differences (e.g. motivated, competitive students versus more casually interested MDs. We cannot know in this case.)

There is a very modest effect of expertise category on criterion ($F(3, 1863) = 3.32, p = 0.02$, partial eta-squared = 0.01). Pairwise comparisons reveal that premedical students are slightly more conservative than medical students ($p = 0.049$). This does not appear to be a particularly meaningful finding.

In terms of the impact of expertise on the effect of block 1 on block 2, the data are noisy, with fewer pairs showing significant effects of block 1 on block 2. This seems to be a statistical power issue. The pairs that are significant are the same as those seen in Figure 4, with low prevalence on block 1 making participants more conservative on block 2 and high prevalence making them more liberal. There is no evidence for any systematic effect of expertise. In particular, there is no evidence that the most expert group (medical students) shows a different pattern of results. In

that group (fortunately, the largest), Pairs with Low Feedback as block 1 are more conservative and with High Feedback as block 1 are more liberal (all $p \leq 0.01$).

Literature Cited

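### The expertise comparison in Figure 9 needs no pair of blocks but was run on pairs, so it leaves out everyone who chose to stop after one block

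*Combined protocol and SAP*

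**What the plan says.** The Methods of the Specific Protocol leave the amount of participation to the individual: "Participants could take part in as many or as few contests as they wished over the course of the six days". After incomplete blocks are dropped, the Observers section reports: "This left 630 participants who ran a total of 277,371 trials in 2,988 blocks". It then removes a further set: "Those participants running only a single block were removed from most analyses because our primary interest is the influence of one block upon the next". Table 4 puts 315 people in the one-block row.

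Under Statistical Analysis / Results, d' and criterion are calculated for each block. A pair is kept only if both of its blocks reach a d' of 0.5.

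The Effects of Expertise section compares d' and criterion across four groups in Figure 9, whatever the prevalence or feedback. Table 6 gives the data by group as numbers of pairs. The d' result is: "There is a highly significant effect of expertise category ($F(3, 1863) = 38.58, p < 0.0001". The text then comments: "It might seem disappointing that MDs were no better at this task than non-medical participants". Among possible reasons for the group differences it mentions "motivated, competitive students versus more casually interested MDs", and adds that the reason cannot be known here.

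**The concern.** The exclusion is justified by the block-to-block question, because one block cannot form a pair. Figure 9 asks something else: whether groups differ in d' and criterion. One complete 80-trial block answers that for its participant.

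Two things are at stake.

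- **Population.** Stopping after one block was the participant's choice. The comparison describes people who continued, while the text speaks of MDs, students and non-medical participants without that limit.
- **Precision.** Expertise varies between people, so the number of people matters more than the number of blocks whenever blocks from one person resemble each other. The statement about MDs is a null result for the smallest of the four groups, and the text gives no confidence interval for it.

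No reported check fills the gap. The first-block-only and all-blocks analyses are reported for the prevalence effect. The repeat of the main analyses uses each person's first pair, which again excludes one-block people. Nothing comparable is reported for expertise.

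**Working it through.** **1. Which records were analysed.** Table 6 pairs: 131 + 952 + 426 + 358 = 1,867. With four groups, error df = 1,867 - 4 = 1,863, exactly as printed for both d' and criterion. The unit is the pair, so one-block participants are absent. Table 6 nevertheless shows 54, 337, 174 and 145 participants, the same as the enrolment counts in Table 1. The number of people actually analysed per group is therefore not reported.

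**2. How many people this leaves out.** Table 4 gives 315.

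- Table 4 rows sum to 872 people: 315/872 = 36%.
- Enrolled, 803: 315/803 = 39%.
- Retained with a full block, 630: 315/630 = 50%.

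These totals cannot all be right. The 872 in Table 4 exceeds the 803 enrolled. Its rows for two or more blocks hold 557 people and 3,094 blocks, more than the 2,988 blocks stated for everyone. If those rows were right and 315 wrong, the share would be (630 - 557)/630 = 12% or (803 - 557)/803 = 31%. All these shares cover all eight expertise categories; none is specific to MDs.

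**3. Effect on precision.** Let ρ be the correlation of d' between blocks of one person. The documents do not give it, so it is an assumption. In units of one block, a person with k blocks contributes k/(1 + (k - 1)ρ). One-block people add 315 in total. The cut in the standard error of a mean from restoring them is 1 - √(C/(C + 315)), where C is the continuers' information. Continuers are credited with all their blocks on both sides, so the cut reflects only the restored people.

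| ρ | C, Table 4 (557 continuers) | Cut | C, 315 continuers | Cut |
|---|---|---|---|---|
| 0 | 3,094 | 4.7% | 2,673 | 5.4% |
| 0.3 | 1,156 | 11% | 654 | 18% |
| 0.5 | 873 | 14% | 493 | 22% |
| 0.8 | 649 | 18% | 367 | 27% |
| 1 | 557 | 20% | 315 | 29% |

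In the fourth column, the ρ = 0 entry is 2,988 - 315 = 2,673 blocks from the text. The other entries scale the Table 4 pattern by 315/557. Expressed as widening from leaving these people out, the first row is 5.0% and 5.7%. It is small because one-block people hold only 315/3,409 = 9% (Table 4) or 315/2,988 = 11% (text) of blocks.

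The range 0.3-0.8 corresponds to assumed between-person SDs of d' of 0.3-0.7 and block-level error SDs of 0.35-0.45. With ρ = τ²/(τ² + σ²), the ends are 0.09/(0.09 + 0.2025) = 0.31 and 0.49/(0.49 + 0.1225) = 0.80.

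**4. Illustration for MDs versus no medical experience.** Assume equal loss in every group and one equally weighted value per person. The 95% half-width is 1.96√(1/n₁ + 1/n₂) person-SDs. With all enrolled (54 and 145) it is 0.31. After a 36% loss (about 35 and 93) it is 0.39. After a 50% loss (27 and 72.5) it is 0.44. This ignores incomplete blocks and the d' filter, so the true numbers analysed would be lower still.

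**The case against.** The strongest case against accepts that pairs were used and disputes how much it matters.

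- **Bias is not shown.** A reader might infer that the MD null is an artefact of who stayed. No performance or stopping data are given by group, so the documents cannot support this. If casual MDs left and motivated ones stayed, the analysed MDs would be the more favourable subset, and they still did no better. Adding the others back would not rescue an MD advantage. This stands: neither the size nor the direction of any bias is known.
- **The text already hedges.** It offers motivation as a rival explanation, calls its expertise categories crude and describes a convenience population. This stands as regards tone, but it does not address an exclusion that the comparison did not need.
- **The gain can be overstated.** Moving from one record per pair to all blocks of all participants cuts the standard error by about 18-20% on Table 4 counts, or 24-28% on 630 people, under the same assumed SDs. A reader might credit all of that to the one-block people. Part of it is the continuers' recovered first block; the figures in the working remove that part.
- **The share is uncertain.** A loss of 36-50% of people might be taken as established. It holds only if the 315 is correct, and the conflicting totals leave that open.
- **A second filter operates.** Requiring a d' of 0.5 in both blocks selects on the very outcome compared. Restoring all blocks without comment would also lift this filter and readmit possible guessers. This stands, so the remedy must treat the two exclusions separately.

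**Conclusion.** The point holds as a defect of a secondary analysis. That Figure 9 excludes one-block participants follows from the printed degrees of freedom and rests on no assumption. The stated reason for the exclusion does not cover this comparison, and no reported check restores these people for it.

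The consequence is a result limited to continuers, with avoidable loss of between-person precision. That loss is about 5% of the standard error with no within-person correlation and about 11-27% for correlations of 0.3-0.8. The range depends on assumed correlations, on the 315 in Table 4, and on the restored blocks passing whatever d' filter is used. The loss among MDs specifically is unknown.

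The documents do not support saying that the MD finding is wrong, that it is biased in a given direction, or that the student advantage would disappear. The block-to-block analyses do need pairs, including the one by expertise, so the main carry-over finding is unaffected.

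**What to change.** 1. Limit the one-block exclusion to the analyses of one block's influence on the next.
2. Run the Figure 9 comparison of d' and criterion on all complete blocks of all participants, with a participant random effect and block type in the model.
3. Add a first-block-only version with one record per person.
4. Report both with and without the d' > 0.5 filter, applied to each block instead of each pair.
5. Give the number of people actually analysed in each expertise group, in place of the enrolled counts in Table 6.
6. State the MD versus non-medical difference with a confidence interval, and base the comment on MDs on that.
7. Reconcile Table 4 with the 630, 803 and 2,988 in the text.

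The cost is a re-run on data already held and posted; no new data are needed. There are three downsides. A single block gives a noisier d', which the model in step 2 weights accordingly. Lifting the d' filter readmits possible guessers, hence the two versions. The random effect may give wider intervals than the printed ANOVA suggests, because its degrees of freedom count pairs as independent.
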